### **3. ENDPOINTS**

As this is an exploratory pilot study to determine the most suitable diagnostic tests for future studies, there will be several endpoints related to (sub)clinical cardiopulmonary dysfunction. Signs of myocardial ischemia, systolic or diastolic dysfunction, rhythm and valve disorders, pericardial effusion and fibrosis, myocardial fibrosis, focal wall motion disorders and coronary calcifications will be analyzed.

The cardiopulmonary (dys)function in EC survivors treated with neo-CRT followed by surgical resection will be compared to cardiopulmonary (dys)function in EC survivors treated with surgical resection alone.

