#### *Patient population*

As many of our EC patients are older and have cardiopulmonary problems as a result of their age, co-morbidities or lifestyle habits, we would like to compare a cohort of patients treated for EC who did or did not undergo (chemo)radiotherapy.

A cohort of these patients is available, as neo-CRT has become standard treatment since 2012 after the publication of the so-called CROSS trial, demonstrating an important survival benefit in the group that received neo-CRT followed by surgery compared to patients treated with surgery alone. During this time period and the time period shortly before and after, patients were treated either with or without neo-CRT. In this time period we did not select patients on cardiopulmonary co-morbidities or age, so we expect comparable groups. Part of these patients were already retrospectively analyzed and compared on short term (within 90 days) morbidity and mortality after resection [23]. These data were published in 2013. We demonstrated an increased incidence of pneumonia and rhythm disorders in patients treated with neo-CRT, but no difference was noted in neither hospital and intensive care unit stay nor in mortality or overall morbidity between these two groups. As these patients were treated in the time period 2000-2012 and thus will have a 5-15 years follow up there is a sufficiently large patient cohort available to prospectively analyze clinical and subclinical cardiac changes and/or toxicities.

*Which tests would be interesting at longer follow up or study parameters*

As mentioned in the introduction, the main focus of this study is (subclinical) cardiopulmonary (dys)functioning. The most important late (subclinical) toxicities we expect to find at longer follow up are: diastolic dysfunction, coronary artery disease, cardiac wall motion disorders, heart failure, pulmonary hypertension, pericardial effusion and/or constriction, cardiac arrhythmia and valve disorders. A number of these endpoints will eventually result in heart failure.

- Anamnesis and physical examinations will be performed in these patients
- In case a pulmonologist or cardiologist has been consulted, additional information will be collected from hospital records of these specialists.
- Radiotherapy treatment parameters will be collected from our database in case the patient was treated with radiotherapy.
- 6 minute walking test
- Echocardiogram
- CT scan
- Cardiac MRI scan
- ECG

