## **2. OBJECTIVES**

Primary Objectives:

The main objective of this study is to determine the most suitable diagnostic test to identify cardiopulmonary (dys)function in EC survivors treated with neo-CRT followed by surgical resection. Furthermore, we want to estimate the difference in cardiopulmonary (dys)function in EC survivors treated with neo-CRT followed by surgical resection compared to EC survivors who were treated with surgical resection alone.

1. To determine the differences in clinical cardiac and pulmonary events, (cardiac ischaemia, heart failure, arrhythmia, valve disorders, pulmonary hypertension, COPD) as clinically diagnosed since treatment between patients treated with neo-CRT and surgery alone.
2. To determine the difference in other (subclinical) parameters as tested by echo cardiogram, 6 minute walking test, CT scan, MRI scan and biomarkers.
3. To analyse the current CAC scores in both patient groups.
4. To determine the difference between the baseline and current CAC scores.

5. To determine the difference between ECG findings currently and on baseline.
6. To correlate the different subclinical imaging parameters to the radiation dose given to the heart and lungs
7. To correlate CAC scores with the given dose distribution on plannings CT scan

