### **4. OTHER STUDY PARAMETERS**

For the purpose of this study, the following parameters will be assessed in all patients:

- Cardiac risk factors
  - Smoking status
  - Age
  - Detailed cardiac history including medical letters from cardiologists when available
  - Detailed pulmonary history including medical letters from pulmonologists when available
  - Alcohol consumption
  - Family history on cardiac events
  - Hypertension
  - D.M.
  - Use of medication
- Combination with chemotherapy
- Postoperative complications and interventions
- Sex
- Daily activities and/or sport

- Original clinical tumor stage (TNM)
- Original tumour length at endoscopy
- Original pathologic tumor stage (TNM)
- Volume (cc) of the irradiated planning target volume
- For irradiated patients; radiotherapy treatment parameters and dose distributions
  - Dose Volume Histogram of the heart
  - Dose Volume Histogram of different cardiac subvolumes
  - Dose Volume Histogram of the lungs

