### **6.3. Exclusion criteria**

- Thoracic radiotherapy for indications other than EC.
- Contra indication for cardiac MRI, pacemaker, cochlear implants, metal not compliant with MRI.

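### The echo, MRI, walking-test and biomarker comparisons take findings as they stand at the visit, with no account of heart or lung disease that predates esophageal cancer treatment

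*Protocol*

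**What the plan says.** **Who is eligible.** Section 6.2 of the protocol sets no condition on earlier heart or lung disease. Section 6.3 excludes "Thoracic radiotherapy for indications other than EC" and "Contra indication for cardiac MRI, pacemaker, cochlear implants, metal not compliant with MRI". The pacemaker item removes only a small part of prior cardiac disease.

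**What is expected of these patients.** The Patient population part of section 1 says that "many of our EC patients are older and have cardiopulmonary problems as a result of their age, co-morbidities or lifestyle habits", and gives this as the reason for a comparison group. On balance between the groups it says: "In this time period we did not select patients on cardiopulmonary co-morbidities or age, so we expect comparable groups".

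**Where timing is used.** Objective 1 in section 2 counts events "as clinically diagnosed since treatment between patients treated with neo-CRT and surgery alone". Objective 4 is "To determine the difference between the baseline and current CAC scores", and objective 5 does the same for ECG findings.

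**Where timing is not used.** Objective 2 asks for the difference in the echo, walking-test, CT, MRI and biomarker parameters, with no baseline. Section 3 lists "Signs of myocardial ischemia, systolic or diastolic dysfunction, rhythm and valve disorders, pericardial effusion and fibrosis, myocardial fibrosis, focal wall motion disorders" and coronary calcifications, with no condition on onset. The Summary places testing at a single time point.

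**Analysis.** Section 10.1 compares means by an independent t-test, with Bonferroni correction if applicable. Section 10.2 tabulates and tests cardiac and pulmonary risk factors between the groups. Section 4 collects, among other items, "Detailed cardiac history including medical letters from cardiologists when available", and the pulmonary equivalent. The protocol does not say how this history enters the section 10.1 comparison.

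**The concern.** A valve lesion known before cancer treatment is left out under objective 1, yet counts in full when the study echo shows it under section 3. The same holds for an old infarct scar on MRI, or for a raised NT-proBNP from long-standing heart failure. One protocol thus treats onset in two ways, and the stricter way is missing from the tests that the study was set up to choose between.

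The main objective is to find the most suitable test for cardiopulmonary dysfunction in patients who had neo-CRT, for use in a later cohort on radiation toxicity. A test that responds mainly to old disease could be ranked too low, because its group contrast is diluted. It could also be ranked too high or too low because the two groups happen to carry different amounts of old disease.

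**Working it through.** The protocol gives no alpha, power, effect size, SD or rate behind its 40 patients, so that figure cannot be reproduced. It also gives no figure for prior disease. Every rate below is an assumption, shown over a range. The only input from the protocol is 20 per group (section 7).

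**1. Which endpoints have a timing reference**

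| Endpoint group | Reference to the time before treatment |
|---|---|
| Clinical events (objective 1) | Yes, only those since treatment |
| CAC (objective 4; section 8.2) | Yes, pre-treatment diagnostic CT |
| ECG, including rhythm (objective 5) | Yes, baseline ECG |
| Echo, MRI, 6-minute walk, biomarkers (objective 2) | None |

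The gap is the last row.

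**2. What 20 per group can detect.** With two-sided alpha 0.05, 80% power and no Bonferroni correction, the detectable difference is (1.960 + 0.842) × √(2/20) = 0.89 SD. There is little room to lose.

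**3. Equal prior disease, yes/no findings.** Let q be the share with prior disease in both groups and p the rate of new dysfunction. The prevalence seen at the visit is 1 − (1 − q)(1 − p), so a true difference shrinks by the factor (1 − q). With p assumed at 10% and 50%, two-sided alpha 0.05 and a normal approximation for two proportions:

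| q | Seen at visit | Difference | Power |
|---|---|---|---|
| 0% | 10% vs 50% | 40 points | 81% |
| 10% | 19% vs 55% | 36 points | 67% |
| 20% | 28% vs 60% | 32 points | 53% |
| 30% | 37% vs 65% | 28 points | 42% |
| 40% | 46% vs 70% | 24 points | 33% |

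**4. Unequal prior disease.** With no treatment effect and p = 10% in both groups, the spurious difference is (1 − p) × (difference in q). That is 0.90 × 0.10 = 9 points, or 0.90 × 0.20 = 18 points.

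**5. Continuous values, which section 10.1 actually compares.** If prior disease shifts a value by δ SD, unequal shares bias the mean difference by δ × (difference in q). For δ = 1 this is 0.10 or 0.20 SD. Equal shares leave the mean difference unbiased if the treatment effect is additive, but they widen the SD to √(1 + q(1 − q)δ²). For q = 25% and δ = 1 this is √1.1875 = 1.09.

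**6. Chance imbalance with equal underlying shares.** For two independent Binomial(20, q) counts:

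| q | Differ by at least 3 patients (15 points) | Differ by at least 4 patients (20 points) |
|---|---|---|
| 15% | 26.3% | 11.8% |
| 25% | 35.9% | 19.9% |
| 35% | 40.7% | 24.5% |

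This is random error. It shows that an observed imbalance is quite likely, not that the comparison is biased.

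**The case against.** There are five points on the other side.

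- **Onset is not ignored throughout.** A reader might infer that every endpoint counts any abnormality whatever its onset. The protocol does not support that: clinical events, CAC and ECG (which covers rhythm disorders and, in part, old infarction) all have a timing reference. This stands, and the point is confined to the remaining tests.
- **Expected comparability is not the only safeguard.** The surgery-alone group is there because of background disease, and section 10.2 would show an imbalance in risk factors. This also stands. But showing an imbalance does not take it out of the section 10.1 comparison, and the comparison group removes background disease only if it is equally common in both groups.
- **Chance imbalance is not bias.** This is correct, because the standard error already covers it. With 8 of 20 against 5 of 20, Fisher's exact p is 0.50; with 9 against 5 it is 0.32. Bias needs truly different shares. The groups were not randomised, and the protocol assumes such a difference away rather than checking its effect.
- **Old and new findings often cannot be separated.** No pre-treatment echo or MRI is described, and specialist letters exist only for some patients. Limiting the main comparison to new findings would mislabel silent old lesions as new, and would discard worsening of old disease after radiation. This stands and shapes the fix.
- **A sensitivity analysis is normally SAP material.** That is true of its details. The protocol itself, however, fixes an onset rule for one set of endpoints, omits it for another, and names an unadjusted test.

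**Conclusion.** The point holds for the echo, MRI, 6-minute walk and biomarker endpoints. Patients with earlier heart or lung disease are eligible, and their findings enter an unadjusted comparison of non-randomised groups, although the protocol uses an onset condition or a baseline for its other endpoints.

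The size depends on prior-disease rates that the protocol does not give. Equal shares of 10% to 40% would shrink a yes/no contrast by the same 10% to 40%. Unequal shares would bias it by roughly nine-tenths of the gap when new dysfunction runs at 10%. For continuous values the bias is the gap in shares times the shift that prior disease causes, which is modest beside the 0.89 SD that the study can detect.

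A reader might go further and conclude that old disease is systematically scored as radiation damage, or that the groups are known to be unbalanced. The protocol shows neither. Section 3 speaks of dysfunction and compares it between groups, and nothing in the document says which group carries more prior disease. This is a change worth making in an exploratory pilot, and it does not invalidate the design.

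**What to change.** Keep these patients eligible and keep the all-patient comparison in section 10.1. Then:

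1. Record for each patient whether cardiac or pulmonary disease was known before cancer treatment. Use the history and specialist letters in section 4 and the baseline ECG of objective 5, and do so before the study images are read.
2. In section 10.1, add the same comparison for the echo, MRI, walking-test and biomarker endpoints without the flagged patients, or adjusted for the flag.
3. In the tables, label categorical findings documented before treatment as pre-existing. Do not limit the main comparison to new findings.
4. State in section 3 that these endpoints describe the condition at the visit, and refer to the added comparison, so that section 3 and objective 1 can be read together.

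The cost is one eCRF field and a second presentation of the same data, with no new tests or patients. There are three downsides. Old records will be incomplete. Silent pre-treatment abnormalities cannot be dated. The restricted comparison is smaller: if 25% were flagged (assumed), 15 per group would remain and the detectable difference would rise from 0.89 to 0.886 × √(20/15) = 1.02 SD. It should therefore be read for consistency with the all-patient result, not as a test in its own right.

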### **4. OTHER STUDY PARAMETERS**

For the purpose of this study, the following parameters will be assessed in all patients:

- Cardiac risk factors
  - Smoking status
  - Age
  - Detailed cardiac history including medical letters from cardiologists when available
  - Detailed pulmonary history including medical letters from pulmonologists when available
  - Alcohol consumption
  - Family history on cardiac events
  - Hypertension
  - D.M.
  - Use of medication
- Combination with chemotherapy
- Postoperative complications and interventions
- Sex
- Daily activities and/or sport

- Original clinical tumor stage (TNM)
- Original tumour length at endoscopy
- Original pathologic tumor stage (TNM)
- Volume (cc) of the irradiated planning target volume
- For irradiated patients; radiotherapy treatment parameters and dose distributions
  - Dose Volume Histogram of the heart
  - Dose Volume Histogram of different cardiac subvolumes
  - Dose Volume Histogram of the lungs

## **5. STUDY DESIGN**

This is a cross sectional pilot study with patients who were or were not treated with neo-CRT.

## **6. STUDY POPULATION**

### **6.1. Population (base)**

Patients with EC treated with or without neo-CRT, alive without evidence of disease, treated between 2000 and 2012 at the University Medical Centre Groningen will be eligible. Twenty patients will be included in both treatment groups. Length of follow up after treatment does not seem to be an important confounding factor as surgery is not considered to be an important risk factor for late toxicity.

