## 1. INTRODUCTION AND RATIONALE

### *Background*

Increasing numbers of patients with intra-thoracic tumours are currently treated with curatively intended combined modality strategies such as chemoradiation (CRT) either in the neo-adjuvant setting followed by surgery or as definitive treatment. Due to improved outcome resulting from the addition of chemotherapy to radiotherapy (RT) and due to the clinical introduction of neo-CRT prior to surgery, the prevalence of EC survivors is rising [5,14,15]. Therefore, the absolute number of patients at risk for treatment-related toxicity is rising as well.

There is increasing evidence that radiotherapy induces cardiac and pulmonary damage. In esophageal cancer patients, pericarditis during and shortly after radiotherapy is the most frequently observed side effect, which should be regarded as an acute inflammatory effect [16] . In the first year after treatment, wall motion disorders with changes in end diastolic volume have been observed [13,17]. These wall motion disorders are most probably caused by changes in the microvasculature. In addition, increased rates of coronary artery disease, myocardial infarctions, heart failure, as well as pericarditis, arrhythmia and valvular disorders have been observed, and may appear after longer latency times [18–20]. Systematic imaging studies analysing subclinical toxicities at longer follow up have never been performed, most probably because of poor survival rates. Preclinical studies indicate cardiopulmonary changes not only relate to the radiation dose given to the heart but also to the dose given to the lung [8,21]. The mechanism behind this phenomenon seems to be an increased pressure in the pulmonary arteries due to vascular fibrosis which leads to diastolic dysfunctioning of the heart due to a volume overload.

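### Protocol section 6.1 dismisses length of follow-up as a confounder for a reason that does not cover age-related and background disease, although objective 1 counts events since treatment

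*Protocol*

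**What the plan says.** Section 6.1 admits patients treated from 2000 to 2012, 20 per group, and says "Length of follow up after treatment does not seem to be an important confounding factor as surgery is not considered" an important source of late toxicity. No other reason is given.

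Elsewhere the protocol says the following:

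- Section 1 (Patient population) says that many of these patients "have cardiopulmonary problems as a result of their age, co-morbidities or lifestyle habits". This is the protocol's own motive for having a surgery-alone comparison group.
- The same text says that "neo-CRT has become standard treatment since 2012". It adds: "During this time period and the time period shortly before and after, patients were treated either with or without neo-CRT". It also says "we did not select patients on cardiopulmonary co-morbidities or age, so we expect comparable groups".
- Section 2, objective 1, concerns differences in cardiac and pulmonary events "as clinically diagnosed since treatment between patients treated with neo-CRT and surgery alone".
- Section 2, objective 4, reads "To determine the difference between the baseline and current CAC scores". It names no groups.
- Section 4 lists age and the main cardiac risk factors, but not years since treatment.
- Section 10.1 gives an unadjusted t-test for parameters summarised as means and standard deviations. Section 10 names no method for event data.

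**The concern.** Time since treatment can affect the group comparison without any late harm from surgery. Patients grow older and acquire coronary disease, arrhythmia, heart failure or COPD whatever their treatment. A count of diagnoses since treatment therefore grows with years at risk in both groups. If one group has been followed for longer, part of any difference in events is only a difference in exposure time.

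The group difference is part of the stated main aim. If surgery-alone patients have the longer follow-up, an excess of events after neo-CRT would tend to be hidden. If the gap runs the other way, the excess would be overstated. With no gap there is no bias from this source.

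Whoever writes the analysis plan from section 6.1 is told that the factor is unimportant, for a reason that does not bear on this route.

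**Working it through.** The protocol gives no event rate and no follow-up distribution by group, so it has no figure of its own to reproduce. From the protocol come the 2000–2012 window and 20 patients per group. Assumed are a constant background event rate of 3% per year (range 2–5%), 7 years in the shorter group (range 7–8) and gaps of 1, 3 and 5 years.

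**Step 1: what gap could the window produce?** Suppose surgery-alone patients are spread evenly over 2000–2012 and neo-CRT patients evenly from year S to 2012. The mean treatment years are 2006 and (S + 2012)/2, so the gap is (S − 2000)/2. That is 0 years for S = 2000, 1 for 2002, 3 for 2006 and 5 for 2010.

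**Step 2: no true effect.** Cumulative incidence is 1 − exp(−rate × years). At 3% per year it is 0.189 at 7 years, 0.213 at 8, 0.259 at 10 and 0.302 at 12. The standard error (SE) of a difference is √[p₁(1−p₁)/20 + p₂(1−p₂)/20].

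| Gap (years) | Shorter v longer | Spurious difference | SE | Difference/SE | Ratio |
|---|---|---|---|---|---|
| 1 | 19% v 21% | 2.4 points | 12.7 points | 0.19 | 1.13 |
| 3 | 19% v 26% | 7.0 points | 13.1 points | 0.53 | 1.37 |
| 5 | 19% v 30% | 11.3 points | 13.5 points | 0.84 | 1.60 |

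Over 2–5% per year and 7–8 years, the spurious ratio is 1.10–1.13, 1.28–1.39 and 1.45–1.63 for gaps of 1, 3 and 5 years. At the corner of 5% per year, 7 v 12 years, the incidences are 0.295 and 0.451. The difference is 15.6 points and the SE is √[(0.295×0.705 + 0.451×0.549)/20] = 15.1 points, so the bias is about one SE there.

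**Step 3: masking of a true effect.** Assume a hazard ratio of 1.5 for neo-CRT and the longer follow-up after surgery alone. Neo-CRT incidence at 7 years is 1 − exp(−0.045 × 7) = 0.270.

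| Gap (years) | Surgery alone | Neo-CRT minus surgery | Over 2–5% per year, 7–8 years |
|---|---|---|---|
| 0 | 0.189 | +8.1 points | +5.9 to +12.2 |
| 1 | 0.213 | +5.7 points | +4.2 to +8.9 |
| 3 | 0.259 | +1.1 points | +0.8 to +2.8 |
| 5 | 0.302 | −3.2 points | −4.3 to −1.6 |

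**Step 4: what the remedy costs in precision.** With equal groups, adjusting for years since treatment multiplies the SE of the group term by √[1 + gap²/(4 SD²)]. For an assumed within-group SD of 2–3 years, the SE rises 1–3% at a 1-year gap, 12–25% at 3 years and 30–60% at 5 years. On person-time at a 3-year gap, expected events in the masking example are 20 × 0.270 = 5.4 and 20 × 0.259 = 5.2. The SE of the log rate ratio is √(1/5.4 + 1/5.2) = 0.61, so the 95% interval spans a factor of exp(1.96 × 0.61) = 3.3 either way.

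**The case against.** Several points on the other side stand.

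- **No gap is documented.** A reader might infer from the 2012 date that follow-up must differ. The protocol does not support that: it says both treatments were in use in the same period, and 2012 dates adoption as standard, not first use. Eligible patients must also be alive and disease-free. Those treated earliest have had longest to drop out, which would tend to shrink the gap. The 5-year case, the only one with a sign reversal, needs every neo-CRT patient to have been treated in 2010–2012.
- **Latency is not confounding.** Section 1 says that "arrhythmia and valvular disorders have been observed, and may appear after longer latency times", and a reader might count this as a second confounder. Latency of radiation damage acts only in irradiated patients. It changes the size of the effect being estimated and does not confound the comparison.
- **The candidate tests.** A reader might infer that the choice of tests for the follow-on cohort is biased. The figures above concern clinical events. No bias is quantified for imaging, biomarkers or the walking test, which measure current status.
- **Age is recorded.** Current age already includes the years elapsed, which partly covers ageing. It is not the same as time at risk: patients of equal age can differ by up to 12 years since treatment.
- **An analysis plan may handle this.** Section 6.1 does not bar adjustment, and silence on methods for event data is no error in a protocol. The point here is a reason that the protocol does state and that does not support its conclusion.

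The expectation of comparable groups does not rescue the sentence. Its ground, no selection on co-morbidity or age, concerns status at treatment and not the years elapsed since.

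**Conclusion.** The point holds in a limited form. The reason in section 6.1 does not cover age-related and background disease in both groups, and objective 1 compares a quantity that accumulates with time. A longer follow-up after surgery alone is plausible but not shown, and it would tend to mask a neo-CRT effect on events.

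On the assumed rates, a 1-year gap matters little. A 3-year gap would remove most of an assumed 1.5-fold hazard from the expected difference. The spurious difference stays below one sampling SE at 3% per year even with a 5-year gap, and reaches about one SE only at 5% per year with that gap. In an exploratory pilot of 40 patients no confirmatory conclusion depends on it. It is worth correcting because the change is cheap and the bias would be systematic. All rates, gaps and the hazard ratio are assumptions.

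**What to change.** 1. Delete the sentence in section 6.1, or correct it to say that time since treatment may differ between the groups and will be examined.
2. Add years since treatment to section 4 and report it by group. It should be derivable from the surgical and radiotherapy databases named in section 8.2.
3. Analyse objective 1 per person-year or as time to event from treatment, and state that the result describes survivors. At a constant rate this removes the bias from a gap. It does not cure the imprecision of about 5 events per group.
4. For the other group comparisons, show an estimate adjusted for years since treatment, age or both beside the unadjusted one, as a sensitivity analysis. Include change in CAC score only if it is compared between groups. The loss of precision worked out above is the reason to show both.

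The cost is a wording change and one derived variable, with no new visit or test.

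Separately, as wording only: the Summary puts testing 5–10 years after treatment and section 1 gives 5–15 years of follow-up. These ranges span 5 and 10 years, while treatment from 2000 to 2012 spans 12 at any one test date. The three statements should be reconciled.
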